excessive lung water volume load should be considered. Increases should begin to make adjustments in fluid therapy and respiratory therapy that are most suitable for patients [28]. However, previous studies are basically aimed at adults, and the number of studies in neonates is very limited. In clinical studies, due to the particularity of neonatal anatomy and physiology, there is a lack of research on the application of severe ultrasound technology in fluid resuscitation of neonatal septic shock. [29] There is an urgent need for an effective non-invasive monitoring method to assist fluid resuscitation in children with septic shock.

At present, the fluid resuscitation methods used in our department for neonates with septic shock mainly include : conventional fluid resuscitation, severe ultrasound-guided fluid resuscitation and NICOM-assisted fluid resuscitation. In this prospective observational study, children with neonatal septic shock diagnosed in the neonatal intensive care unit of Guangdong Second People 's Hospital from January 1,2022 to December 31,2023 were included in the study. According to the different monitoring methods used in shock treatment, 30 cases of severe ultrasound-assisted fluid resuscitation, 30 cases of NICOM-assisted fluid resuscitation and 30 cases of conventional fluid resuscitation were collected, a total of 90 cases. The hemodynamic differences, NICU hospitalization time, renal replacement therapy / mechanical ventilation, and 28-day mortality were compared among the three groups to comprehensively evaluate the application value of cardiopulmonary ultrasound and non-invasive cardiac output in fluid resuscitation of neonatal septic shock. Improve the therapeutic effect of neonatal septic shock, enrich the application field of clinical ultrasound, and promote the cross-fusion of ultrasound and pediatrics, and provide clinical basis for subsequent prospective studies.

二、 research objective

1. Main Objective: To study the application value of severe ultrasound and non-invasive cardiac output technique in fluid resuscitation of neonatal septic shock.

2.Secondary purpose: To promote the therapeutic effect of neonatal septic shock and enrich the application field of clinical ultrasound technology.

三、 Research Design Types, Principles, and Test Procedures

1. Research Design

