In this study, children with neonatal septic shock diagnosed in the neonatal intensive care unit of the Second People 's Hospital of Guangdong Province from January 1,2022 to December 31,2023 were included. According to the different monitoring methods used in routine / clinical shock treatment, 30 cases of severe ultrasound-assisted fluid resuscitation, 30 cases of NICOM-assisted fluid resuscitation and 30 cases of routine fluid resuscitation were collected. The demographic data, blood examination and microbiological examination data of the three groups at admission were collected. The fluid volume, blood lactic acid, blood pressure, vasoactive drugs (such as dopamine and epinephrine / norepinephrine), mechanical ventilation, renal replacement therapy and antibiotic use before fluid resuscitation were collected. The cumulative fluid infusion volume during fluid resuscitation (6 hours), and the use of vasoactive drugs and mechanical ventilation for 6 hours were collected. NICU hospitalization time, cumulative hospitalization time and mortality were collected.

四、 case selection

1. Inclusion criteria:

1 Born less than 28 days on admission; 2 Conform to the diagnostic criteria for neonatal septic shock in the ' 2020 International Guidelines for Saving Sepsis Campaign: Management of Septic Shock and Sepsis-related Organ Dysfunction in Children; 3 For children diagnosed with septic shock, fluid resuscitation should be performed according to the routine diagnosis and treatment. 4 The legal guardian has signed the informed consent.

2. excluded criteria:

1 combined with neurogenic shock, trauma and hemorrhagic shock; 2 symptomatic patent ductus arteriosus; 3 combined with congenital heart disease; 4 give up treatment or death within 24 hours of admission; 5 The legal guardian refused to participate in the study; 6 Key information and information missing.

3. Elimination criteria

Subjects who have been enrolled in the study but meet one of the following criteria should be excluded :

(1) After inclusion, those who did not meet the inclusion criteria or met the exclusion criteria were found.

(2) Those who have not used test drugs / interventions.

4. Standard for suspension of research

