Measurement data and count data were expressed as mean \pm standard deviation [or median (interquartile range)] and percentage (%), respectively. Normal and non-normal distribution data were analyzed by two independent sample t test and Mann-Whitney U test, respectively. The chi-square test was used to compare the count data rates between groups. Kaplan-Meier method was used to draw the survival curve, and Log-rank test was used to compare the difference of 28-day cumulative survival rate between the two groups. Baseline covariates were adjusted in the Cox proportional hazards model to calculate the hazard ratios (HRs) and their 95 % confidence intervals. Logarithmic conversion was performed on hospital stay and organ support time and linear regression analysis was used to calculate a 95 % confidence interval for reporting. No data with missing information is interpolated. The above statistical analysis was performed using R software, and the test was bilateral, and $p < 0.05$ was considered statistically significant.

十一、 Ethics in clinical research

Clinical research will follow the World Medical Congress ' Helsinki Declaration ' and other relevant provisions. Before the study began, the clinical study was carried out after the ethics committee approved the test plan. Before each subject is selected for this study, the researcher has the responsibility to fully and comprehensively introduce the purpose, procedure and possible risks of this study to the subjects or their agents, and to sign a written informed consent form. The subjects should be informed that they have the right to withdraw from the study at any time. Informed consent should be retained as a clinical research document for review. The personal privacy and data confidentiality of the subjects will be protected during the study.

十二、 Research progress

January 1, 2022 - March 31, 2022 : Pre-project preparation, harmonization of data collection standards, training of personnel

From April 1,2022 to May 31,2023 : the specific implementation stage of the experiment, case data were collected.

From June 1,2023 to December 31,2023 : Write scientific research papers and project summary reports 1 Organize research data and conduct statistical analysis ; 2 writing and submission of scientific research papers ; 3 Summarize the research results and write the project summary report.

十四、 reference

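### Three groups are compared on three unranked main outcomes, but the tests are two-sample, one is worded for two groups, no pairs are named, and nothing covers several tests at 0.05

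*Combined protocol and SAP*

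**What the plan says.** - **Design.** Section 三 (Research Design) states that "30 cases of severe ultrasound-assisted fluid resuscitation, 30 cases of NICOM-assisted fluid resuscitation and 30 cases of routine fluid resuscitation were collected". Section 一 (Research background) adds that outcomes including "28-day mortality were compared among the three groups".
- **Main outcomes.** Section 七 lists NICU stay, cumulative hospital stay and mortality as main criteria and does not rank them.
- **Tests.** Section 十 (Statistical processing), repeated in the abstract's statistical row, says "Normal and non-normal distribution data were analyzed by two independent sample t test and Mann-Whitney U test, respectively", and then "Log-rank test was used to compare the difference of 28-day cumulative survival rate between the two groups". For rates it says "The chi-square test was used to compare the count data rates between groups", without limiting the number of groups.
- **Models.** "Baseline covariates were adjusted in the Cox proportional hazards model to calculate the hazard ratios (HRs) and their 95 % confidence intervals". For log-transformed stay and organ-support time, "linear regression analysis was used to calculate a 95 % confidence interval for reporting".
- **Level.** "the test was bilateral, and $p < 0.05$ was considered statistically significant". There is no overall three-group test for continuous data, no list of pairs, no deciding analysis and no rule for several tests.
- **Aim.** The abstract's goal sets ultrasound against conventional resuscitation. The main objective in section 二 covers ultrasound and NICOM.

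**The concern.** A two-sample test cannot compare three groups until someone says which two, and the plan does not. A log-rank test described as between two groups does not fit a three-group study. The aim does not settle the matter, because the abstract and section 二 disagree on whether NICOM is under evaluation. The analyst must therefore choose the pairs and the lead outcome, possibly after seeing the data.

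The 5% in the plan is a per-test level. With several pairs and three main outcomes, the chance that some comparison falls below 0.05 when nothing differs is well above 5%. What is at stake is how far a significant result on a main criterion can be believed as evidence for a monitoring method.

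**Working it through.** **1. The plan's own figure.** 3 groups × 30 = 90, which agrees with the stated total. The documents give no power, effect size, standard deviation or event rate behind 90, so nothing further can be reproduced.

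**2. Wording side by side.** Sections 一, 三, 五 and 六 speak of three groups. The log-rank sentence in section 十 and the abstract speaks of two. The abstract also describes the admission data as coming from two groups where sections 三, 五 and 六 say three. Leftover text from a two-group version is therefore plausible, but the statistical section still has to be corrected.

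**3. Number of tests.** Three groups give 3 × 2 / 2 = 3 pairs. With one test per outcome and pair:

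- all pairs: 3 × 3 = 9 tests
- the two monitors against conventional: 2 × 3 = 6 tests
- one pair: 1 × 3 = 3 tests

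**4. Reference values if the tests were independent,** from 1 − 0.95^m:

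- m = 9: 1 − 0.630 = 0.370
- m = 6: 1 − 0.735 = 0.265
- m = 3: 1 − 0.857 = 0.143

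**5. Allowing for dependence.** The pairs share groups and the two stays are correlated, so the true rates are lower. They were simulated with no difference between groups and 30 per group (20,000 runs in each of 12 scenarios). The documents do not give the inputs, so these are assumptions: 40% mortality (section 一 cites more than 40% for septic shock), log-normal stays, correlation between the stays of 0.3 to 0.95, and deaths that either end the stay at about 7 days or leave it unaffected.

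| Family at unadjusted 0.05 | If independent | Simulated |
|---|---|---|
| Nine tests | 37.0% | 19.3–30.9% |
| Six tests | 26.5% | 14.7–24.0% |
| Three tests | 14.3% | 8.5–13.8% |

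A simpler simulation (t tests on both stays, chi-square on mortality, stay correlation 0 to 0.95, death not shortening the stay) gives about 25–33% for nine tests. It also gives about 12% for three pairs on a single outcome.

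**6. What the error rate does not cover.** Groups follow the monitoring used in care. Suppose no monitor has any effect but case mix alone gives 45% against 35% mortality. With 30 per group the standard error is √(0.2475/30 + 0.2275/30) = 0.126, so the expected z is 0.10/0.126 ≈ 0.79. A single pre-named chi-square test then rejects about 12% of the time. At 50% against 35%, the standard error is √(0.25/30 + 0.2275/30) = 0.126, z ≈ 1.19, and rejection is about 22%.

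**The case against.** **Two-sample tests are a normal way to compare three groups in pairs.** This stands. Only the log-rank sentence literally contradicts the design. For t and Mann-Whitney, the defect is that no pairs are named and no overall test is given. The chi-square, Cox and regression analyses can all take three groups.

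**The study is observational, calls no test confirmatory and is meant to inform later work.** This also stands, and it limits the severity. But the plan sets a significance threshold and applies it to main efficacy criteria, so its p-values will be read as evidence.

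**The abstract already points to ultrasound against conventional.** It does not call this the primary contrast, section 十 does not carry it forward, and section 二 conflicts with it. Even that one pair has three outcomes, hence 8–14%.

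**A reader might infer that the inflation is much larger,** because mortality has chi-square, log-rank and Cox analyses and each stay has a raw test and a log-linear regression, any of which might decide. The documents do not support that. Section 十 gives the Cox and linear models an estimation role (hazard ratios and confidence intervals), and it ties covariate adjustment to Cox alone. Larger rates that rely on an adjusted log-linear model as a rival test assume an analysis the plan does not state. If either of the two named mortality tests may decide, the ranges barely move: about 20–32%, 15–25% and 9–14%.

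**A reader might also infer that fixing one pair, one outcome and one test makes 5% the error rate of a conclusion about a monitor.** It does not, because the groups are not randomised (step 6 of the working).

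**Conclusion.** Wrong as written, and should be fixed. The log-rank wording contradicts the three-group design. The t and Mann-Whitney tests have no named pairs, no overall test and no rule for several tests. The abstract's goal conflicts with the main objective.

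With one test per outcome and pair, the chance of at least one false positive is about 19–31% for all nine pairwise tests, 15–24% for the two monitors against conventional and 8–14% for one pair. These ranges rest on the assumed mortality, stay distribution and correlations, and on no case-mix difference between groups. The wording conflict and the omissions do not depend on them. The defect limits the weight that a p-value below 0.05 can carry; it does not invalidate the study.

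**What to change.** In section 十 and the abstract's statistical row:

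1. Change two groups to three. Specify ANOVA or Kruskal-Wallis, a 3×2 chi-square test, a log-rank test on 2 degrees of freedom, and a three-level group factor in the Cox and log-linear models.
2. Name one primary outcome and the one analysis that decides it. A baseline-adjusted model with covariates listed in advance is preferable, because the groups are not randomised. Test the outcome globally at 0.05 and run its pairwise tests at 0.05 only if the global test is significant. With three groups this is a closed procedure, so the pairwise tests need no further adjustment. Report the other two main criteria as secondary, with estimates and 95% confidence intervals. If the investigators will not name a primary outcome, declare the analysis exploratory and base no claim of effect on p < 0.05.
3. Reconcile the abstract's goal with the main objective in section 二.
4. State that controlling for several tests does not remove confounding by choice of monitor, so 5% is not the error rate of a causal conclusion.

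**Cost.** No new data. Two main criteria in section 七 become secondary; which one leads is the investigators' choice. The gate costs power. For ultrasound against conventional with 30 per group (unadjusted chi-square, assumed rates), power at 40% against 20% mortality falls from 39% to 28% if NICOM mortality lies midway, 31% if it equals conventional and 32% if it equals ultrasound. At 40% against 10%, it falls from 80% to 68–77%.

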Clinical research protocol

Project name: Application of severe ultrasound in fluid resuscitation of neonatal septic shock

leading unit: Guangdong Second Provincial General Hospital

project leader: [name]

Department: Pediatrics

Research period: January 1,2022 to December 31,2023

NCT No.: none.

Version No.: V3.0

Version Date: November 29, 2021

Abstract

object name	Lung ultrasound-guided fluid resuscitation in neonatal septic shock
goal of study	In this study, a prospective observational study was conducted to compare the effects of severe ultrasound-assisted fluid resuscitation and conventional fluid resuscitation on the prognosis of children with neonatal septic shock, so as to evaluate the application value of the two techniques in fluid resuscitation of neonatal septic shock.
research design	
n this study, children with neonatal septic shock diagnosed in the neonatal intensive care unit of the Second People 's Hospital of Guangdong Province from January 1,2022 to December 31,2023 were included in the population. According to the different monitoring methods used in conventional / clinical shock treatment, 30 cases of fluid resuscitation assisted by severe ultrasound, 30 cases of fluid resuscitation assisted by NICOM and 30 cases of conventional fluid resuscitation were collected, a total of 90 cases.
 
(1) The demographic data, blood examination and microbiological examination data of the two groups at admission were collected.
 
(2) The fluid volume, blood lactic acid, blood pressure, vasoactive drugs (such as dopamine and epinephrine / norepinephrine), mechanical ventilation, renal replacement therapy and antibiotic use were collected before fluid resuscitation.
 
(3) The cumulative fluid infusion volume during fluid resuscitation (6 hours), and the use of vasoactive drugs and mechanical ventilation for 6 hours were collected.
 
(4) NICU hospitalization time, cumulative hospitalization time and mortality were collected.

Total number of cases studied	90 cases (30 cases in each group)
case selection	
Inclusion criteria:
 
1 Born less than 28 days on admission; 2 Conform to the diagnostic criteria for neonatal septic shock in the ' 2020 International Guidelines for Saving Sepsis Campaign: Management of Septic Shock and Sepsis-related Organ Dysfunction in Children; 3 For children

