	
diagnosed with septic shock, fluid resuscitation should be performed according to the routine diagnosis and treatment. 4 The legal guardian has signed the informed consent.

	
excluded criteria:
 
1 combined with neurogenic shock, trauma and hemorrhagic shock; 2 symptomatic patent ductus arteriosus; 3 combined with congenital heart disease; 4 give up treatment or death within 24 hours of admission; 5 The legal guardian refused to participate in the study; 6 Key information and information missing.

Treatment plan	
This study was an observational study. Clinicians developed a diagnosis and treatment plan based on the treatment plan for neonatal sepsis in the sixth edition of " Practical Neonatology " and the " International Guidelines for the 2020 Saving Sepsis Campaign: Management of Septic Shock and Sepsis-related Organ Dysfunction in Children. "

efficacy evaluation	
The main efficacy indicators: hospitalization time and cumulative hospitalization time, mortality.
 
Secondary efficacy indicators: cumulative fluid volume during fluid resuscitation, use of vasoactive drugs and mechanical auxiliary gas.

	
Safety evaluation index: Mortality.

statistical method	
Measurement data and count data were expressed as mean \pm standard deviation [or median (interquartile range)] and percentage (%), respectively. Normal and non-normal distribution data were analyzed by two independent sample t test and Mann-Whitney U test, respectively. The chi-square test was used to compare the count data rates between groups. Kaplan-Meier

	
method was used to draw the survival curve, and Log-rank test was used to compare the difference of 28-day cumulative survival rate between the two groups. Baseline covariates were adjusted in the Cox proportional hazards model to calculate the hazard ratios (HRs) and their 95 % confidence intervals. Logarithmic conversion was performed on hospital stay and organ support time and linear regression analysis was used to calculate a 95 % confidence interval for reporting. No data with missing information is interpolated. The above statistical analysis was performed using R software, and the test was bilateral, and $p < 0.05$ was considered statistically significant.

Research period
	
January 1, 2022 – December 31, 2023

一、 Research background

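### Groups follow the monitor used in routine care, but baseline adjustment is stated only for the Cox model, so the 6-hour outcomes would be compared unadjusted

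*Combined protocol and SAP*

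**What the plan says.** The Abstract (Treatment plan) describes the design: "This study was an observational study. Clinicians developed a diagnosis and treatment plan". Research Design (section 三.1) and research method (section 五) form the three groups by the monitor used in ordinary shock care. No matching, weighting, stratification or propensity method appears anywhere.

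Statistical processing (section 十), repeated in the Abstract, gives these methods:

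- Continuous data: "Normal and non-normal distribution data were analyzed by two independent sample t test and Mann-Whitney U test, respectively".
- Rates: "The chi-square test was used to compare the count data rates between groups".
- Survival: Kaplan-Meier curves, the log-rank test and a Cox model: "Baseline covariates were adjusted in the Cox proportional hazards model to calculate the hazard ratios (HRs) and their 95 % confidence intervals". The covariates are not named.
- Durations: "Logarithmic conversion was performed on hospital stay and organ support time and linear regression analysis was used". No covariates are mentioned.
- Missing data: "No data with missing information is interpolated".

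The efficacy section (section 七) makes NICU stay, cumulative stay and mortality primary. Six-hour fluid, vasoactive use and ventilation are secondary. Observation items (section 六) collects fluid, lactate, blood pressure, vasoactive drugs, ventilation and renal replacement before resuscitation.

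**The concern.** The Abstract sets out to "compare the effects of severe ultrasound-assisted fluid resuscitation and conventional fluid resuscitation on the prognosis of children with neonatal septic shock", and the Research background says that "NICU hospitalization time, renal replacement therapy / mechanical ventilation, and 28-day mortality were compared among the three groups". These are comparative claims from groups that clinicians' choices created. An observational design is legitimate, but it leaves confounding control to the analysis, and the plan states that control only for survival.

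The 6-hour outcomes are especially exposed because they repeat items recorded just before resuscitation. An infant already ventilated is likely to be counted as ventilated at 6 hours whichever monitor was used. If one group starts sicker or with more support, an unadjusted 6-hour difference partly reflects that starting point. The baseline data that could help separate the two are collected but have no stated use for these outcomes.

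**Working it through.** **1. Outcomes matched to stated methods**

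| Outcome | Stated method that fits | Adjustment stated? |
|---|---|---|
| 28-day survival | Cox (with Kaplan-Meier, log-rank) | Yes, covariates unnamed |
| NICU and cumulative stay | Log-linear regression | Not stated |
| 6-hour fluid | t or Mann-Whitney test | Not possible in these tests |
| 6-hour vasoactive or ventilation use, as yes/no | Chi-square test | Not possible in this test |
| The same two items, as durations | Log-linear regression, if read as organ support time | Not stated |

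**2. The plan's own figure.** 3 × 30 = 90, which agrees with the stated total. The documents give no effect size, SD, event rate or group imbalance, so nothing else can be reproduced. Everything below rests on assumed inputs and on no true effect.

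**3. Fluid volume, two groups of 30.** Let D be the severity imbalance in SD and r the correlation of severity with fluid. The standardised shift is D × r / √(2/30), and the rejection rate is P(|Z + shift| > 1.96). For D = 0.5, r = 0.5: 0.25 / 0.258 = 0.97, giving 0.162. The simulations used 8,000 runs.

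| D, r | Formula | t test | Mann-Whitney | Linear model with covariate |
|---|---|---|---|---|
| 0.2, 0.3 | 0.056 | 0.054 | 0.050 | 0.050 |
| 0.2, 0.5 | 0.067 | 0.066 | 0.064 | 0.050 |
| 0.5, 0.3 | 0.089 | 0.094 | 0.088 | 0.054 |
| 0.5, 0.5 | 0.162 | 0.158 | 0.145 | 0.048 |
| 0.8, 0.3 | 0.153 | 0.147 | 0.140 | 0.050 |
| 0.8, 0.5 | 0.341 | 0.329 | 0.310 | 0.049 |

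An overall test of three groups, with severity shifted by 0, half and all of D, rejected 0.056 to 0.259 unadjusted and 0.046 to 0.052 adjusted.

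The last column assumes one confounder measured without error. With measurement reliability 0.7 the adjusted rate was 0.050 to 0.073; with 0.5 it was 0.049 to 0.119.

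**4. Yes/no ventilation, 30 versus 30.** The 6-hour rate is p × (proportion continuing) + (1 − p) × (proportion newly starting), where p is the proportion ventilated beforehand. With 95% continuing and 20% starting, p = 0.4 gives 0.38 + 0.12 = 0.50, and p = 0.6 gives 0.57 + 0.08 = 0.65. Chi-square rejection rates are exact.

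| Ventilated before | Continue / start | 6-hour rates | Chi-square | Continuity-corrected | Logistic with pre-resuscitation value |
|---|---|---|---|---|---|
| 40% vs 60% | 95% / 20% | 0.50 vs 0.65 | 0.217 | 0.148 | 0.067 |
| 40% vs 50% | 95% / 20% | 0.50 vs 0.575 | 0.092 | 0.054 | 0.070 |
| 40% vs 60% | 80% / 30% | 0.50 vs 0.60 | 0.123 | 0.077 | 0.056 |
| 40% vs 50% | 80% / 30% | 0.50 vs 0.55 | 0.069 | 0.039 | 0.053 |

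With equal 6-hour rates of 0.50 the chi-square test rejects 0.052, or 0.027 corrected. For three groups at 40/50/60% beforehand, the overall chi-square test rejects 0.165 (95%/20%) or 0.099 (80%/30%). Logistic regression with the pre-resuscitation value rejects 0.062 or 0.056.

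**5. Hospital stay.** No error rate is claimed. In a simulation with about 41% mortality and death ending the stay, the same kind of imbalance gave about 5% without adjustment.

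**The case against.** The strongest reply is that the reach is narrow. Survival already has an adjusted model, and the regression for stay could carry covariates even though none are mentioned. The firm gap therefore concerns secondary process measures. If vasoactive and ventilation use are analysed as durations, they too fall under that regression, which leaves 6-hour fluid as the only unconditional case. This stands as a limit on scope, but it does not remove the gap: the plan does not say whether the support outcomes are yes/no or durations, and states no covariates for the regression.

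The second reply is that every input to the illustration is assumed, and the results run from negligible to large. With 40% versus 50% ventilated beforehand, the corrected chi-square test rejects 5.4% or 3.9%, against 7.0% or 5.3% for logistic regression. That is correct: with a mild imbalance and the corrected test, adjustment does not lower the error rate. The correction applies only to two-by-two tables, so it does not help an overall three-group comparison, and the imbalance cannot be known in advance.

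Third, the reason for choosing a monitor is not among the listed data, so adjustment cannot be complete. That also stands, and it limits what the adjusted results can claim.

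**Conclusion.** The concern holds and should be fixed. The text establishes that groups are not randomised, that adjustment is stated only for survival, and that the tests fitting 6-hour fluid and yes/no support cannot adjust. It does not establish that severity differs between groups, or that the log-linear regression will be unadjusted.

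The size is conditional. Under the assumed imbalances, false-positive rates for fluid run from about the nominal 5% to about one in three. For yes/no ventilation they run from 7% to 22% uncorrected, or 4% to 15% corrected. Adjustment brings fluid back to about 5% only when the main confounder is well measured.

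**What to change.** Before analysis, name a short covariate list from data already collected, for example pre-resuscitation lactate, blood pressure and one maturity or weight measure if recorded. Use it with the three-level group factor in:

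1. a linear model for 6-hour fluid (log scale if skewed), also including pre-resuscitation fluid;
2. logistic models for vasoactive and ventilation use if these are yes/no, each including its own pre-resuscitation value, after stating whether they are yes/no or durations;
3. the log-linear models for NICU stay, cumulative stay and organ support time;
4. the Cox model already planned.

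Report the t, Mann-Whitney and chi-square results as descriptive, and word conclusions as adjusted associations. Death shortening the stay needs separate handling. With mortality of 40% versus 20% and no imbalance, the log-linear model rejected about 20% with or without the covariate.

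**Cost.** Wording and modest analysis work, with no new data unless a maturity or weight measure is missing from the demographic data.

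- Precision: in the fluid simulations, standard errors went from 12% smaller to 4% larger.
- Small samples: logistic tests with four covariates reject 6% to 7%, so the list must stay short.
- Sparse cells: if 95% of ventilated infants continue and 45 of the 90 start ventilated (12 + 15 + 18), all continue with probability 0.95^45 ≈ 0.10. The baseline coefficient then has no finite estimate, although the group term does.
- Missing data: with three covariates plus the pre-resuscitation value, each missing independently in 5%, 90 × 0.95⁴ ≈ 73 infants remain; at 2%, 90 × 0.98⁴ ≈ 83. Some of this loss may already occur through exclusion criterion 6, which removes infants lacking key information.
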